4. Response: In addition to the Sacramento VA data, the Sepulveda VA data are presented in Tables 3 and 5. Data collected by our collaborator, [name] at the Phoenix VA, confirm the water method increases ADR (overall and in the proximal colon, particularly diminutive ones). The abstract will be presented at the DDW – ASGE Oral Session on Cutting Edge Colonoscopy Technology 2011. Thus, comparable observations demonstrating the water method to exert a positive impact on ADR have been forthcoming from three VA sites. To highlight the importance of the water method, this technique is being featured in two symposia in the upcoming DDW in May 2011 where the water method will be presented and discussed in special topic forum and symposium on cutting edge colonoscopy technology. Important publication including an *Endoscopy Innovation Forum* paper will be published. We have organized two Colorectal Cancer Screening Symposium at the Sacramento VAMC where the water method was presented and its application and benefits discussed.

5. Response: We have limited the number of secondary outcomes. They include overall adenoma detection rate, cecal intubation success rate and sedation medication requirement. We will monitor a number of quality measures to insure the three groups of patients are comparable.

6. Response: The sample size calculation is based on the primary outcome of proximal diminutive ADR. Additional observations will be used as hypothesis-generating for future studies.

7. Response: Permission will be sought from the IRB to contact the patients at 30 days by phone and if patients report that they have had complications including ER visit or hospital admission, follow up data will be obtained (with the patients' permission) from the computerized patient record or from the local admitting hospital. It is important to track the 30 day complications since patients have been admitted to local hospital because of post procedural pain not associated with perforation but possibly due to the large amount of air insufflated especially in those who had air insufflation colonoscopy.

8. v) **Sample size:** Response: Based on more preliminary data collected in a RCT supported by the ASGE on ADR with the combined chromoendoscopy and water method, we have recalculated the number of subjects required for the study.

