Population studies showed that traditional air colonoscopy failed to eliminate post screening colonoscopy cancers or cancer mortality in the proximal colon. Even diminutive adenomas harbor significant dysplasia. A simple, inexpensive, easy-to-learn method of adding indigocarmine to the water method may increase the yield of proximal diminutive adenomas. A higher ADR may minimize the burden of interval CRC by decreasing missed adenomas. The current study evaluates the benefits of a combined chromoendoscopy and water method for screening colonoscopy in identifying proximal diminutive adenomas compared to the water method alone and the conventional air method. The long term goal is to perform further studies to determine if post screening colonoscopy interval cancers and cancer mortality in the proximal colon can be attenuated among the veteran population by the novel methods.

(b) Hypothesis

In patients undergoing optical colonoscopy for first time CRC screening, a higher proximal diminutive ADR (proportion of patients with at least one diminutive adenoma in the colon proximal to the splenic flexure) will be found in the group examined by combined chromoendoscopy (indigo carmine) with water method compared with water method alone or air method.

Primary outcomes: Proximal diminutive (<10 mm) adenoma detection rate.

Secondary outcomes: ADR (overall for entire colon and for proximal colon), cecal intubation success rate, sedation medications.

Co-variables: patient demographic variables [age, gender, BMI, co-morbidity, endoscopic findings, etc.], successful completion of split bowel preparation

(c) Specific Objectives

To compare the primary and secondary outcomes in a prospective RCT involving the combined chromoendoscopy with water method vs. water method alone and air method in asymptomatic patients undergoing first time outpatient screening colonoscopy.

Short title: Comparative efficacy of water & indigo carmine vs. water or air method on ADR – a RCT

Long title: RCT to compare proximal diminutive adenoma detection rate (ADR) of combined chromoendoscopy (Indigo carmine) with water infusion in lieu of air insufflation (water method) vs. water method alone or conventional air method in screening colonoscopy

(1) Rationale

Statement of the Problem

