If the cecum is believed to have been reached, but the usual landmarks are not recognizable, more water is infused to distend the cecum to aid visualization of the appendix opening. The volume of infused water, the use of position change and abdominal compression will be recorded. Once the appendix opening is visualized, air insufflation will be used to distend the cecum to confirm touching of the cecal floor with visualization of the ileocecal valve and/or the appendix orifice (cecal intubation). Thereafter, usual air insufflation will be used to facilitate suctioning of residual colonic content (mostly water and residual feces) and mucosal inspection, biopsies or polypectomy during endoscope withdrawal. All polyps (including diminutive ones in the right colon) will be removed and tissue submitted for pathological evaluations. When multiple diminutive polyps (predominantly hyperplastic) in the rectum are identified and recorded; a limit of one biopsy will be taken (to minimize time burden on study subjects).

Reassuringly, water enemas using equivalent volumes were not associated with significant fluctuations in serum electrolytes [63]. Preliminary data did not show any significant change or differences in the serum electrolytes level before and after the water infusion (Table 8) [58]. With the suction of dirty water and then infusion of clean water during scope advancement, the actual amount of water within the colon at any time during scope insertion is much less than the total volume of water used to facilitate scope passage.

The combined chromoendoscopy with indigo carmine and water method: As used in pilot study, the technique is identical to the water method above except we add 10 ml of 0.8% indigo carmine solution into a liter bottle of sterile water to make up a solution of 0.008% indigo carmine [22].

b. Population to be studied

Inclusion criteria: asymptomatic veterans scheduled for first time screening colonoscopy and agree to be randomized will be enrolled.

Exclusion criteria: patients who decline to be randomized, non screening cases.

c. Unit(s) of analysis (Table 10).

Table 10: Primary and secondary outcome variables

Measures	Details
Primary Outcome	
Proximal diminutive adenoma	1 = yes, 0 = no
Primary covariates	
Demographic variables	Age, gender, BMI, ethnicity
Volume of water (ml)	ml used during colonoscopy
Cecal intubation time*	Time from anus to cecum (appendix opening, ileocecal valve seen)

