Withdrawal time*	Time from cecum to anus
Total procedure time*	From insertion of colonoscope to removal from the anus
Completion of split preparation	Yes = 1, no = 0
Secondary covariates	
Colon cancer	Colon cancer discovered during exam (Yes = 1, no = 0)
Sedation medications	Type, initial dose, additional doses during colonoscopy based on patient pain score and request
Secondary Outcomes	
Size of adenoma*	mm measured by open forceps
Anatomical location of adenoma	rectum, sigmoid, descending, splenic, transverse, hepatic, ascending, cecum
Located behind a fold*	Yes = 1, no = 0
Morphology of lesion*	Polypoid or flat
Pathologic diagnosis of the biopsy or snared polypectomy specimen	Adenoma (with or without advanced features), hyperplastic polyp, serrated adenoma
Immediate complications	Perforation, bleeding, hypoxia, hypotension, arrhythmia
Complications up to 30 days	Perforation, bleeding, hypoxia, hypotension, arrhythmia, severe abdominal pain requiring ER visit and/or admission to hospital

* Documented during colonoscopy and objective confirmation by digital video record of endoscope clock.

Record keeping: A digital image capturing system will be used to record the procedure to document the procedure times (insertion, arrival in the cecum, biopsy, polypectomy, end of examination), confirmation of cecal intubation (visualization of the appendix orifice and/or the ileocecal valve) and the findings during the withdrawal phase (recorded by the research assistant). The digital images will bear no personal identifier.

d. Sampling strategy

[figure not shown]
The consent covers agreement to allow the colonoscopist to randomize the method to aid colonoscope insertion and examination (chromoendoscopy with water vs. water method vs. air insufflation), and to video record and photograph the procedure for analysis.

In order to accommodate the patients and allow them time to complete the split bowel preparation in the morning of the procedure, the study procedures will be scheduled as late morning and early afternoon cases as this will give the patients more time to complete the bowel preparation.

Sample size calculation

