Demographic data interview & record review (co-variables)	X		
Medical and surgical history (co-variables)	X		
Complications - emergency department visit, hospitalization (co-variables)			X

(g) General analytic plan (statistical analysis):

Primary Hypothesis.

In patients undergoing sedated colonoscopy for screening, when all polypoid and flat lesions including diminutive ones proximal to the splenic flexure are removed by polypectomy or biopsy, the patients examined by the combined chromoendoscopy and water method will be found to have a higher proportion of individuals with at least one proximal diminutive adenoma compared with the water method alone or air insufflation method for aiding insertion of the colonoscope.

Statistical Analysis: We will summarize the variables collected by calculating the frequencies of the categorical variables [such as number of patients with at least one proximal diminutive adenoma (proximal diminutive ADR), number of adenomas detected, adenoma location, adenoma size, gender, ethnicity, etc) and calculating the mean and standard deviation of the continuous variables (such as adenoma size, volume of water used, age, BMI, etc)].

To investigate differences in ADR, we will use logistic regression models, with an outcome that is a binary variable denoting whether each subject had one or more diminutive proximal adenomas. These models will allow us to quantify the differences between the three tests and determine if the differences are statistically significant. We will account for demographic characteristics (age, gender, BMI, ethnicity, etc) and investigate how other primary covariates (procedure time, volume of water used in study, etc) affect the rate of adenoma detection. Following, we will investigate the effects of secondary covariates (colon cancer detected, sedation medications) on adenoma detection rates.

As a secondary analysis, we will investigate how the secondary outcomes vary among the three tests. We will use repeated measures ANOVA and logistic regression models to quantify the differences between tests and to determine if they are statistically significant.

Pitfalls and solution

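### The documents give two conflicting sets of secondary outcomes, and the analysis section does not say which set will be compared between the arms

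*Combined protocol and SAP*

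**What the plan says.** Specific Aims, (b) Hypothesis, gives the list as "Secondary outcomes: ADR (overall for entire colon and for proximal colon), cecal intubation success rate, sedation medications". Sedation is not among the co-variables named in that same section.

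Response to reviewers, Critique 2, item 5, says that the secondary outcomes have been cut back and adds "They include overall adenoma detection rate, cecal intubation success rate and sedation medication requirement". It does not mention proximal ADR.

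Under Unit(s) of analysis, "Table 10: Primary and secondary outcome variables" has a block of seven secondary outcomes: lesion size, site, position behind a fold, shape, histology, immediate complications and complications to 30 days. Sedation medication is in the block of secondary covariates, detailed as "Type, initial dose, additional doses during colonoscopy based on patient pain score and request".

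Table 11, under Data collection methods, labels cecal intubation and total medication as secondary outcomes. It also has the row "Complications - emergency department visit, hospitalization (co-variables".

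The General analytic plan will examine "the effects of secondary covariates (colon cancer detected, sedation medications) on adenoma detection rates", and then compares the secondary outcomes across the three methods without naming them. The response to Critique 3, item 3, gives lesion size and location as examples of secondary outcomes.

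**The concern.** A secondary analysis is pre-specified only if a reader can tell beforehand which variables it covers. Here the reader cannot. An analyst working from the Specific Aims would compare overall ADR, proximal ADR, intubation success and sedation. An analyst working from Table 10 would compare lesion features and complications. Both could claim to have followed the plan.

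This matters more than usual because one unblinded operator, who is also the principal investigator, performs every examination. The section on blinding of the endoscopist holds back all analysis until the last patient has been evaluated. That protects the conduct of the examinations but does not settle which list applies once the data are open. The same section promises blinded evaluators for secondary outcomes where indicated, and the scope of that promise also depends on the list.

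The second problem is sedation. A variable affected by the randomised method should be compared between arms. In a model for detection that also contains the arm, it can absorb part of the arm effect or distort it.

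**Working it through.** No formula applies, so the check sets the places side by side.

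| Measure | Specific Aims (b) | Critique 2, item 5 | Table 10 | Table 11 | Critique 3, item 3, and General analytic plan |
|---|---|---|---|---|---|
| Overall ADR | secondary outcome | named | no row | inside a general findings row | not named as a secondary outcome |
| Proximal ADR | secondary outcome | not named | no row | inside a general findings row | not named as a secondary outcome |
| Cecal intubation success | secondary outcome | named | no row | secondary outcome | not named |
| Sedation medication | secondary outcome | named | secondary covariate | total: secondary outcome; additional: quality measure | secondary covariate |
| Lesion size, location | not listed | not listed | secondary outcomes | inside a general findings row | given as examples of secondary outcomes |
| Fold, shape, histology | not listed | not listed | secondary outcomes | inside a general findings row | not named as secondary outcomes |
| Immediate complications | not listed | not listed | secondary outcome | no row | not named |
| 30-day complications | not listed | not listed | secondary outcome | emergency visits and hospitalisation: co-variable | not named |

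**Counts.** The Specific Aims have three domains, or 4 measures when ADR is split into entire and proximal colon. Table 10 has 5 lesion features + 2 complication rows = 7. The overlap is 0, so the union is 4 + 7 = 11.

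**Cecal intubation.** The only entry in Table 10 is a duration, "Time from anus to cecum (appendix opening, ileocecal valve seen", classed as a primary covariate. Success is nevertheless a secondary outcome in the Specific Aims, Critique 2 and Table 11. The quality-control section on missed lesions also counts patients with failed intubation as failures by intent-to-treat.

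**Unit of analysis.** The Specific Aims measures are one value per patient. Table 10's lesion rows, such as size ("mm measured by open forceps"), can occur several times in a patient. The General analytic plan names repeated measures ANOVA and logistic regression for the secondary outcomes without assigning either. Repeated measures suits the lesion rows, whereas a single yes/no per patient needs ordinary logistic regression. The choice of list therefore also changes the model.

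**Sedation.** Three places make it an outcome (Specific Aims, Critique 2, Table 11) and two make it a covariate (Table 10, General analytic plan). The envelope is opened immediately before the procedure, and additional doses are given during it on the patient's request. The part that varies by patient therefore arises largely after randomisation. The response to Critique 1, item 3, lists a lower medication requirement among the advantages of the water method, so the sponsor expects a difference by arm.

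**The case against.** The strongest reply is that the intended list is not really in doubt. Specific Aims (c) sets the objective of comparing primary and secondary outcomes directly after giving the list. Table 11 and the intent-to-treat rule support cecal intubation as an outcome. The General analytic plan does not cite Table 10. The location and histology rows of Table 10 supply the data from which overall and proximal ADR can be derived.

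Much of this stands, and it rules out a stronger reading. A reader might infer that overall ADR, proximal ADR and intubation success will never be compared between arms. The documents do not support that: it follows only if Table 10 governs, and nothing says that it does. But nothing says that the Specific Aims govern either, and the response to Critique 3 points the other way. Data from which ADR could be derived are not the same as a defined per-patient outcome.

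It can also be said that a variable may be compared between arms and explored as a predictor as well. That is true, and the sedation models come after the main three-arm comparison. The difficulty is limited to arm contrasts taken from a model that contains sedation.

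Finally, a reader might infer that Table 11 turns all complications into covariates. Its label covers only emergency visits and hospitalisation up to 30 days. The immediate complications of Table 10 have no row there.

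**Conclusion.** The contradiction is real and can be confirmed line by line. The Specific Aims, largely supported by Critique 2 and Table 11, conflict with Table 10, which Critique 3 and the General analytic plan follow in part. None of the four Specific Aims measures is an outcome in Table 10, sedation has conflicting roles, and 30-day complications are an outcome in one table and partly a co-variable in the other. The conclusion is that the plan leaves the secondary comparisons unfixed, not that any particular comparison has been dropped.

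The effect is confined to the secondary analyses. The primary outcome is the same in the Specific Aims, Table 10, the sample size section and the General analytic plan, and the sample size rests on it alone. The union of 11 measures shows how much room there is for choice; it is not an error rate, and the documents allow none to be calculated. The size and direction of any distortion from adjusting for sedation cannot be worked out from the documents. That part of the point rests on the sponsor's own expectation that sedation need differs by method. The inconsistency should be corrected before any analysis starts.

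**What to change.** Reconcile the lists to the Specific Aims:

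1. **Table 10.** Add per-patient rows for overall ADR (1/0), proximal ADR of any size (1/0), cecal intubation success (1/0, with failures counted by intent-to-treat as already stated) and sedation medication. State which dose measure is analysed.
2. **General analytic plan.** Name these four as the secondary outcomes, with logistic regression for the three binary measures and ANOVA for sedation dose.
3. **Sedation.** Remove it from the secondary covariates in Table 10 and from the between-arm ADR models in the General analytic plan.
4. **Lesion features.** Label size, location, fold, morphology and pathology exploratory, and keep repeated-measures methods for them only. Critique 2, item 6, already treats additional observations as hypothesis-generating. State that the response to Critique 3, item 3, is superseded.
5. **Complications.** List them as safety outcomes in both tables.

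The cost is rewording two tables and the secondary-analysis and covariate text, plus a note on the Critique 3 response. No new data, patients or procedures are needed. The price is that the lesion-level features lose secondary status. The primary outcome and sample size do not change.

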The pain score (0=none, 10=most severe) is assessed at all stages of the colonoscopy. At intervals of 2-3 minutes the nurse will ask the patient if s/he needs more medication and the pain score. If the pain score is ≥2, the endoscopist will perform maneuvers to minimize the pain such as reducing loops by shortening of the colonoscope, suction of colonic content as well as abdominal compression. When asked by the nurse if s/he wants additional medications, the patient has the option of declining or accepting the pain medications offered. If the patient approves receiving additional medication, 25 µg of fentanyl or 1 mg of midazolam will be administered. All medications will be documented [16].

Gold standard to ensure no lesions are missed (quality control)

To reduce the rate of missed polyps, colonoscope withdrawal time will be maintained at >6 minutes [46] in all groups, even though there is some controversy over this specific recommendation [47,48]. Patients who fail cecal intubation will undergo CTC [61,62]. These patients will be considered failures of cecal intubation based on intent-to-treat analysis for the index colonoscopy.

Colonoscopist

A single colonoscopist (PI) who has been responsible for developing the pilot data at the Sacramento VAMC will perform all of the study cases in this single center study to obviate the confounding factor of variations in ADR amongst colonoscopists.

a. Intervention/treatment/services to be compared

Equipment: High definition variable stiffness pediatric colonoscopes (Olympus), water infusion pump (Endolav EL-100C, Cooper Surgical, Trumbull, CT), suction device, biopsy forceps, snares for polypectomy, video and photographic instruments will be used for the study. The same instruments will be employed for both the study and control patients. Water at body temperature (37°C maintained by water bath) will be used.

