Issues related to blinding of endoscopist. The colonoscopist and nurse cannot be blinded to treatment allocation and the primary outcome of proximal diminutive ADR. Randomly selected (10% of total determined by the statistician) coded digital records will be reviewed by independent paid observers to confirm agreement of lesions, cecal intubation, times (endoscopic clock) of insertion, cecal intubation and total withdrawal of the colonoscope. For secondary outcomes, to compensate for increased risk of investigator bias, this study will be designed to use independent, blinded evaluators, whenever indicated, for assessment of outcome(s). No analysis will be started until all patients have completed evaluation to avoid biasing the colonoscopist, who may change the approach if it is known that one group is doing better or worse than the other.

Issues related to male dominance in enrollees. While patients of both sexes will be enrolled, it is likely that there will be a predominance of male enrollees. This is unavoidable because the VA population consists of 95% male and 5% female.

Issue related to differential dropout rate. Since sedation is provided for all groups of patients, we expect the patient tolerance will be similar. Any dropouts will be retained in the data analysis (intent-to-treat) and labeled treatment failures (no adenomas in the unexamined segment) to avoid any differential dropout rate to seriously bias outcomes.

Issues related to the water techniques used to insert the colonoscope lack standardization. The insertion technique for the water method will be standardized (56) by having the air pump turned off until the cecum is reached. Air pockets are suctioned on scope insertion. Dirty water is suctioned before clean water is infused to facilitate scope advancement and to minimize the volume of water inside the patient in case the patient becomes incontinent. Close attention will be paid to keep record of these variables to detect unavoidable variations.

(I) Publication from Last Funding Period (Pertinent Publications)

RESEARCH PAPERS - PEER REVIEWED

[name], Mann S, Leung FW. Option for screening colonoscopy without sedation – a pilot study in United States veterans. *Alimentary Pharmacology and Therapeutics* 2007; 26(4):627-631.

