The study methods both utilize water infusion in lieu of air insufflation with sedation, with the addition of dye to the combined chromoendoscopy and water method. Indigocarmine has been used and recommended in the literature for chromoendoscopy to enhance detection of colon polyps.

Exclusion criteria for safety include patients who decline to participate, unable to give informed consent or complete the questionnaires due to language or other difficulties.

All patients will be seen by one of the site investigators or the research staff prior to enrollment.

After participant enrollment, one of the site investigators will review blood pressure, cardiac rhythm and pulse oximetry (oxygenation) safety parameters prior to participant enrollment.

A study physician will be available on site for managing adverse events.

The site investigators will monitor study subjects for adverse events during the study.

Monitoring for pain in both study and control method groups will be carried out as follows: During the examination (with the colonoscope tip in the rectum, sigmoid colon, splenic flexure, transverse colon, hepatic flexure, ascending colon and cecum) or at 2-3 minute intervals, the patient will be asked to report pain on 10 point scale (0 = no pain, 10 = maximum pain) and for those who receives sedation, patient will be asked if additional medications are needed for control of pain. Additionally, if a pain score of ≥ 2 is recorded, medications will be offered. In either instance, the patient can decline or accept the medication depending on whether the pain is tolerable or not.

Monitoring for blood pressure, cardiac rhythm and pulse oximetry (oxygenation) will be maintained throughout the entire colonoscopy. Devices with automatic alarms used on a routine basis for all colonoscopy patients will be employed. Any alarm signals will be attended to immediately by a member of the research team and appropriate action will be taken to resolve any safety issues.

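### Sedation medication is a named secondary outcome but is filed and analysed as a covariate for ADR, and two sections word the rule for asking about and responding to pain differently, so its comparison between arms is not clearly planned and is open to bias

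*Combined protocol and SAP*

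**What the plan says.** **Role of sedation as an outcome.** Specific Aims (b) lists "Secondary outcomes: ADR (overall for entire colon and for proximal colon), cecal intubation success rate, sedation medications", and Specific Aims (c) sets the objective: "To compare the primary and secondary outcomes in a prospective RCT". The response to reviewers (Critique 2, item 5) says of the secondary outcomes: "They include overall adenoma detection rate, cecal intubation success rate and sedation medication requirement". Table 11 marks total medications during colonoscopy as a secondary outcome and additional medications as a quality measure.

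**Role of sedation as a covariate.** Table 10 places sedation medications under secondary covariates and not among its secondary-outcome rows. The general analytic plan, section (g), follows the table: "we will investigate the effects of secondary covariates (colon cancer detected, sedation medications) on adenoma detection rates".

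**How doses come to be given.** Under the sedation protocol during colonoscopy, pain is scored throughout. "At intervals of 2-3 minutes the nurse will ask the patient if s/he needs more medication and the pain score". Then, "If the pain score is ≥2, the endoscopist will perform maneuvers to minimize the pain". Human Subjects (5), Safety and Monitoring, has pain scored at seven named colon locations or at 2-3 minute intervals, with a question about medication. It then adds: "Additionally, if a pain score of ≥ 2 is recorded, medications will be offered". In both sections the patient may accept or decline.

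**Who knows the arm.** On blinding, the section on other issues says "The colonoscopist and nurse cannot be blinded to treatment allocation". The randomisation section says that patients are blinded, with their eyes covered on insertion.

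**The concern.** An outcome that is also a covariate in the same plan leaves the analyst to choose between two instructions. If Table 10 is taken as the working list, sedation is used to explain ADR and nobody is clearly told to compare it between arms, although that comparison is a stated objective. The result is likely to be of interest, because the response to reviewers (Critique 1, item 3) already credits the water method with a lower medication requirement.

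The covariate use raises a separate problem. Additional doses are given after allocation and may depend on the method. Adjusting the ADR comparison for them no longer estimates the full effect of the randomised method on detection.

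Finally, the amount of sedation depends partly on when the patient is asked and what follows a given score. Two wordings, applied by staff who know the arm and may expect a benefit, leave room for the rule to be applied differently across arms.

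**Working it through.** The plan states no figure for the sedation outcome, so the check is mainly textual.

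**1. Which list does the secondary analysis follow?** Section (g) says that secondary outcomes will be compared among the three methods, without listing them there. Two lists are available.

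| Source | Role of sedation |
|---|---|
| Specific Aims (b); response to reviewers, Critique 2 item 5 | secondary outcome |
| Table 11 | total: secondary outcome; additional: quality measure |
| Table 10 | secondary covariate |
| Section (g) | covariate for ADR |

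Two details point towards Table 10 as the list intended for the secondary analysis. The response to reviewers (Critique 3, item 3) illustrates secondary outcomes by adenoma size and location, which are Table 10 rows. The methods named in section (g), repeated measures ANOVA and logistic regression, suit several lesions per patient or yes/no results. Neither suits one medication total per patient. No sedation variable is defined for analysis, although several drugs are given.

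**2. Is sedation a post-randomisation variable?** Table 10 includes additional doses given during colonoscopy. The envelope is opened immediately before the procedure, so additional doses follow allocation. Section (g) brings sedation in after the main covariates, as a further step. Whether the reported ADR treatment effect would come from that model is not stated.

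**3. Do the two pain rules differ?**

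| | Sedation protocol | Safety and Monitoring |
|---|---|---|
| Enquiry | throughout, with questions every 2-3 minutes | seven locations, or every 2-3 minutes |
| Asked about medication at enquiry | yes | yes |
| Score of 2 or more | manoeuvres by the endoscopist | medication offered |
| Who decides on medication | patient | patient |
| Differs by arm | not stated | same for study and control groups |

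The differences lie in the enquiry schedule and in the response to the same score. The rest overlaps.

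**4. What one extra dose amounts to.** Sedation generally starts with 25 µg fentanyl and 1 mg midazolam (plus 50 mg diphenhydramine). An accepted request adds 25 µg fentanyl or 1 mg midazolam. The total for that drug becomes 25 + 25 = 50 µg, or 1 + 1 = 2 mg, which is double. If the starting dose is the same in every arm, an arm difference in totals equals the arm difference in additional doses.

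**5. Can the schedules be turned into a number of enquiries?** Only with assumed times, because the plan gives no insertion times. For an assumed 5 to 15 minutes, enquiries = minutes / (2 to 3), which runs from 5/3 = 1.7 to 15/2 = 7.5, against seven locations. This leaves out withdrawal, and an enquiry is not a dose. It shows that the schedules can differ, not that the comparison is biased.

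**The case against.** The strongest reply is that the two pain sections can be read together. Both ask about medication at routine enquiries, so a patient scoring 2 or more is asked about it under either. The safety section does not exclude manoeuvres, and the colonoscopy section permits them for all patients at the colonoscopist's discretion. Allocation is concealed in sealed opaque envelopes, patients are blinded and decide for themselves, and neither section distinguishes between arms. An ambiguous rule applied equally adds noise, not bias. This largely stands. A reader might infer that an arm difference in sedation cannot be attributed to the method at all, and the documents do not support that. What remains is that unblinded staff control the timing and reason for an offer. The planned 10% review of recordings covers lesions, cecal intubation and times, not offers.

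A reader might also infer that a longer procedure in one arm confounds the comparison because it brings more enquiries. It does not: procedure length is a consequence of the randomised method and part of its total effect on sedation.

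On Table 10, its secondary-outcome rows also omit overall ADR and cecal intubation success, so omission alone does not show that sedation has been dropped. Section (g) has a general commitment that could cover it. The inference that sedation would go unanalysed is therefore too strong. Sedation is, however, the only one of the three that the table positively assigns to another role.

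Lastly, the response to reviewers (Critique 2, item 6) says that the trial is sized on the primary outcome and treats additional observations as hypothesis-generating. That limits the weight of the point but does not remove the inconsistency.

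**Conclusion.** The point holds in limited form. Sedation medication has conflicting roles, its comparison between arms is not clearly planned, and ADR may be conditioned on a variable measured after randomisation. The covariate listing does not itself distort the sedation comparison, because it concerns the ADR models only. Separately, the two pain sections differ in enquiry schedule and in the response to a score of 2 or more. With staff aware of the arm, the sedation comparison is open to bias, but it is not uninterpretable.

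Neither the size nor the direction of any bias can be derived from the documents. It would require staff to apply the wording differently by arm, which is possible but not shown. The only size available is that one accepted increment doubles the usual starting amount of that drug. The definition of the primary outcome and the planned 330 patients (110 per arm) are unaffected. The matter should be corrected, but it does not threaten the main conclusion.

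**What to change.** 1. In Table 10 and section (g), move sedation medication from secondary covariates to secondary outcomes, in line with Specific Aims (b) and Table 11. Keep it out of the models that estimate the ADR treatment effect.
2. Define the outcome as total medication per patient, separately by drug, which is the Table 11 outcome. Compare it between arms with a method for one value per patient, giving arm differences with confidence intervals. Report additional doses alongside, as the Table 11 quality measure, and do not substitute them for the total.
3. Reconcile the sedation protocol and the Safety and Monitoring section into one enquiry schedule and one response to a pain score of 2 or more, worded identically for all three arms. Which rule to adopt is a clinical decision on which this review takes no view.
4. Tabulate by arm the manoeuvres, medications and maximum pain scores that the plan already collects, so that readers can judge whether the rule was applied evenly.

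The cost is protocol wording and one table correction, with no added patients or procedures.
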